#### 7.2.1 Replacement of Patients

Patients who discontinue trial product or withdraw from the trial will not be replaced.

### 7.3 Lost to Follow-up

A patient will be considered lost to follow-up if he or she repeatedly fails to return for scheduled visits and is unable to be contacted by the trial site.

#### 8 TRIAL ASSESSMENTS AND PROCEDURES

- The following sections describe the trial assessments and procedures, while their timing is summarized in the flowchart (see Section 1.2).
- Informed consent must be obtained before any trial-related activity, see Section 10.1.4.
- All screening evaluations must be completed and reviewed to confirm that potential patients meet all inclusion criteria and none of the exclusion criteria.
- The Investigator will maintain a screening log to record details of all patients screened and to confirm eligibility or record reason for screen failure, as applicable.
- At screening, patients will be provided with a patient card stating that they are participating in a trial and giving contact details of relevant site staff that can be contacted in case of emergency.
- Adherence to the trial design requirements, including those specified in the flowchart, is essential and required for trial conduct.
- Patients will be provided with patient diaries to register administrations of trial product, PS use (SBS-IF only) as well as fluid intake and urinary output during 48-hour periods prior to site visits.
- Review of patient diaries, PRO questionnaires, ECG, laboratory reports etc. must be documented either on the documents or in the patient's source documents. If clarification of entries or discrepancies in the patient diary or PRO questionnaires is needed, the patient must be questioned, and a conclusion made in the patient's source documents. Care must be taken not to bias the patient.
- During the trial, blood samples will be collected from all patients for efficacy, safety, PK and ADA assessments. The total blood volume drawn per patient amounts to a maximum of approximately 530 mL, including all assessments described in Sections 8.2 and 8.3. The samples are collected over a period of approximately 59 weeks (1 year and 1.5 months).
- Repeat samples may be taken for technical issues and unscheduled samples or assessments may be taken for safety reasons. Please refer to Appendix 2 (see section 10.2) for further details on laboratory samples.

### 8.1 Demographics and Other Baseline Characteristics

#### 8.1.1 Demographics

Demographic information to be collected includes date of birth, gender, race, and ethnicity.

### 8.1.2 SBS Characteristics and History

Information about the patient's SBS includes the following characteristics:

- The underlying cause of SBS
- Date of diagnosis of underlying disease
- Date of SBS diagnosis

- Remaining bowel sections [30]; whether patient has a colon-in-continuity (jejuno-colic anastomosis/SBS anatomical group 2, jejuno-ileo-colic anastomosis/SBS anatomical group 3, or other), an end-jejunostomy/SBS anatomical group 1, ileostomy/SBS anatomical group 1, or colostomy, presence of ileocecal valve, the surgery dates and reason(s) for resection, this includes the most recent resection
- Bowel lengths; length of the remnant small bowel, the remnant colon in percent (according to Cummings classification [31])
- Severity of SBS based on the ESPEN Functional and Clinical Classification of Chronic Intestinal Failure (8)
- Date that the patient started PS, if applicable

# 8.1.3 Body Weight and Height

Body weight (kg with 1 decimal accuracy) will be measured at all visits. Height (cm) will be measured at screening only.

Weight will be measured on a calibrated scale. Patients should wear light clothing and no shoes. Stoma bags should be emptied prior to the measurement.

Patients should be encouraged to measure their body weight at home weekly to detect potential signs of fluid retention early (before edema becomes readily visible). If the weight changes, patients should be instructed to call the site for guidance.

# 8.1.4 Medical History/Concomitant Illness

Medical history information to be collected includes all ongoing conditions and relevant/significant medical history (including all major hospitalizations and surgeries).

Details of whether the patient suffered from any of the following will be recorded: Encephalopathy, ascites, cholestasis, steatosis, and/or cirrhosis. If yes, the outcome / histopathologic diagnosis and date of histopathologic diagnosis will be recorded.

Concomitant illness must also be captured and noted as to relatedness to SBS.

The patient's history of drug and/or alcohol abuse, information on tobacco smoking (never smoker (<100 cigarettes or equivalent /lifetime), current smoker, or former smoker) and current alcohol use will also be captured.

### 8.1.5 Concomitant Medication

All prescription and non-prescription medications taken within 7 days prior to and including the screening visit will be recorded in the eCRF. Any changes to concomitant medications that occur throughout the trial will be recorded (see Section 6.5).

All relevant previous treatments, including treatment with teduglutide, any other GLP-2 analogs or native GLP-2 are recorded in the eCRF.

### 8.1.6 Colonoscopy

Patients with a remnant colon are required to have a colonoscopy as part of the screening procedures and the follow-up visit (Week 56). Colonoscopy results must be available for Visit 1. Colonoscopies performed up to 6 months prior to screening are acceptable. If a remnant colon is

present, but a colonoscopy may not be appropriate, a CT scan, CCE or MRI will suffice at the discretion of the Investigator.

# 8.1.7 COVID-19 Management

The COVID-19 pandemic is expected to exist during the conduct of the trial. In case the situation worsens, the following mitigating actions may be implemented, as applicable:

- Site visits (Visit 2 and forward) can be converted to phone/video calls to obtain and record information about:
  - o AEs
  - o Body weight (patient's home scale is acceptable)
  - Procedures and changes to concomitant medication
  - Urine and blood samples for safety assessments (may be collected at a local community laboratory, patient's general practitioner or by a home nurse at the Investigator's discretion)
  - Pregnancy, planned pregnancy and missed menstruation, if any. For females of childbearing potential a pregnancy urine dipstick kit will be shipped to patient's home from the site.
  - O Adherence to PS regimen in the diary (see Section 6.4.1) as per standard practice (including volume, and content) and modify weekly PS volume and schedule in accordance with section 8.2.9 in the protocol.

### • PROs:

- Ocopies of PGIC, SBS-I and EQ-5D-5L questionnaires can be sent to the patients for completion, including the standard instructions for how to complete, date, and sign. The instructions include among other things the following notes; It is important the SBS-I is completed by the patient without assistance of family members.
- o Patients should:
  - Fill in the PROs and complete the questionnaires on the same day as the remote visit is scheduled, but prior to the site visit call.
  - Send a copy of completed PROs to site for review and entry into eCRF.
  - Bring original documents to site at next possible visit. These documents will be source data to be verified at that point. If source data is lost, then copies received will suffice.
- Trial product can be sent directly from the site to the patient's home
- Visit 9 can be postponed, until on-site visit is possible again. After 24 weeks of treatment, the patient will be in a stable treatment, and postponing the visits is not expected to affect the assessments
- The EoT visit can be postponed (time window can be extended up to + 8 weeks)

Deviations from the protocol caused by circumstances related to the pandemic will be documented. Handling of data affected by the pandemic situation will, if applicable, be addressed in the statistical analysis plan.

# 8.2 Efficacy Assessments

Planned time points for all efficacy assessments are provided in the flowchart (Section 1.2). Assessment of the primary and key secondary endpoints will be based on metabolic balance studies, described in Section 8.2.1. During the metabolic balance studies, as well as before trial visits, the patients will adhere to an individual fixed drinking menu, described in Section 8.2.2, associated with measurements of urine volume, described in Section 8.2.3.

# 8.2.1 Metabolic Balance Study

The metabolic balance study measures the total intake and output of energy, macronutrients (lipids, carbohydrates, proteins [nitrogen as a marker]) and micronutrients. The oral diet intake (i.e. food and fluids) are assessed by duplicate meals and liquids by quantification of weight, volume, as well as the content of energy, macronutrients and electrolytes. During the metabolic balance study, the patients will collect duplicate portions of all intake solid and liquid in buckets covering 24-hour periods. Likewise, all output (i.e. ostomy output, diarrhea and urine production) will be collected and quantified. The content of the buckets will be weighed, processed into dry matter by laboratory techniques and subsequently analyzed at the site's local laboratory.

Before the metabolic balance study is started, a fixed drinking menu will be set which will be followed for the metabolic balance study at Visits 1 and 9 (see Section 8.2.2).

The 48-hour metabolic balance study will start at 8:00 in the morning. If the patient receives PS at baseline, the 48 hours should preferably cover a day on PS (first day) and a day off PS.

The procedure for the metabolic balance study is listed below:

- The laboratory technician will inform the patient about collection of diet and liquid intake, urine and feces and hand out bottles and buckets that will be used for the collection.
- The collection will be performed for 48 hours.
- The patient will collect oral diet intake corresponding to the type and amount ingested. Wrapping paper, plum stones, chicken bones and similar will not be collected.
- Each day, bottles and buckets will be picked up by the laboratory technician.

Table 6 specifies the samples collected.

Table 6 Sample Collection during Metabolic Balance Study

| Sample             | To be collected in | Handling and storage               |
|--------------------|--------------------|------------------------------------|
| Urine              | Bottle             | No special handling or precautions |
| Feces              | Bucket             | Feces will be stored in a freezer  |
| Oral liquid intake | Bottle             | No special handling or precautions |
| Oral food intake   | Bucket             | No special handling or precautions |

The content of the bottles/buckets will be weighed, processed into dry matter by laboratory techniques and subsequently analyzed at the laboratory. Details of the techniques used are published (32).

The analyses performed on the collected material are presented in Table 7.

 Table 7
 Analyzes on Collected Material in Metabolic Balance Study

| Analysis  | Samples                       | Method  |
|---|-------------------------------|---|
| Weight/volume   | Urine, feces, food an liquid  | Weight/measuring cylinder   |
| Energy content  | Feces, food and liquid        | Bomb calorimetry  |
| Fat (aliphatic compounds)                               | Feces, food and liquid        | Titration   |
| Carbohydrates   | Feces, food and liquid        | Englyst's method (33)   |
| Nitrogen (as a marker of protein)                       | Urine, feces, food and liquid | Kjeldahl's method (34)  |
| Sodium and potassium                                    | Feces, food and liquid        | Flame photometry  |
| Calcium and magnesium                                   | Feces, food and liquid        | Atomic absorptiometry   |
| Sodium, potassium, calcium, magnesium, urea, creatinine | Urine                         | 
 
Sodium (potentiometri)
 
Potassium (potentiometri)
 
Calcium (calculated as a product of the urine calcium concentration and 24h urine volume)
 
Magnesium (calculated as a product of the urine magnesium concentration and 24h urine volume)
 
Urea (calculated as a product of the urine carbamide concentration and 24h urine volume)
 
Creatinine (absorption photometry)
 
 |

### 8.2.2 Fixed Fluid Intake

The oral liquid intake should be kept constant during the metabolic balance study, ensuring that potential changes in any output measurements are not caused by changes in liquid intake. Therefore, during the screening phase, patients will be instructed to in detail documenting their 24-hour fluid intake, specifying sort (water, tea, milk, coffee etc.), amount (mL) and time of intake.

The patients must follow their drinking menu on metabolic balance study days during hospital admissions (Visit 1 and Visit 9) and during the 48-hour pre-visit urine collection periods at home prior to each visit, excluding Visit 1 and 9. As stated above, the drinking menu starts on the same day/time as the 48-hour pre-visit urine collection, and lasts for a total of 48 hours. After Visit 9, the patients are no longer restricted to a fixed drinking menu during the 48-hour periods, but they should instead drink an amount that reflects their preferred or habitual fluid intake. They must only drink the same fluid items as in the drinking menu and must record their intake as well as their urine output.

Solid oral food intake is unrestricted and may be varied according to the patients' own choice.

### 8.2.3 48-hour Urine Volume

Urine volume will be recorded by the patient in his or her patient diary during the defined 48-hour measurement periods prior to a trial visit and transcribed to the eCRF. During this time the patient must adhere to the individually predefined drinking menu (up to Visit 9, see Section 8.2.2). The patient will be provided with urine measuring cups.

The 48-hour urine volume measurements should occur as close as possible to and within 7 days of the coming site visit. For patients with SBS-IF the measurements should be timed with the PS schedule. Patients on PS 7 days weekly must perform the 48-hour measurement on 2 consecutive

days on PS. Patients on PS 1-6 days weekly must record the 48-hour measurement at 1 day on PS and 1 day off starting on the day on PS.

See Table 8 for further clarity. The grey boxes indicate the possible 48-hour urine measurement periods. If more than 1 interval is available anyone of them can be chosen.

The patient should perform the 48-hour measurement on the same days of the week during each period as long as the PS regimen remains the same. The selected days will be recorded in the patient diary. If the PS regimen changes during the trial, a new schedule for 48-hour measurement can be chosen.

PS days/ Week 48-hour measurement Day 1 Day 2 Day 3 Day 4 Day 5 Day 6 Day 7 7 days 2 days on PS 3 6 days 1 day on PS + 1 day off PS 1 5 days 1 day on PS + 1 day off PS 1 2 3 5 4 days 1 day on PS + 1 day off PS2 3 3 days 1 day on PS + 1 day off PS2 2 days 1 day on PS + 1 day off PS2 1 day 1 day on PS + 1 day off PS0 days 2 days off PS

Table 8 Timing of 48-hour periods and balance studies

# 8.2.4 Patient Diary

Patients will be required to complete diaries throughout the course of the trial. Patients will record the following:

- Details regarding trial product administration, including date and time of the day as well as injection site area used, i.e. abdomen or thigh
- PS use (SBS-IF only) including bag name, volume and infusion date on an ongoing basis
- Urine volume and oral fluid intake will be recorded by the patient during the defined 48-hour periods prior to a trial visit
  - The patient should perform the 48-hour measurement on the same days of the week during each period as long as the PS regimen remains the same. The selected days will be recorded in the patient diary.
- If the PS regimen changes during the trial, a new schedule for 48-hour measurement can be chosen and recorded in the patient diary

The Investigator (or designee) must review the patient's diary entries routinely throughout the entire trial period. If clarification of entries or discrepancies in the diary is needed, the patient must be questioned, and a conclusion made in the patient's medical record and in the diary. Care must be taken not to bias the patient.

### 8.2.5 Absorption of Wet Weight/Fluids

During both 48-hour metabolic balance studies (Visit 1 and Visit 9), the duplicate meal and liquid intake and the total excretion of stomal output and/or diarrhea will be collected and weighed. Absorption of wet weight/fluids is calculated as oral intake (liquid and solid) minus fecal output. Absolute intestinal wet weight absorption (g/day) = oral wet weight intake (liquid and solid) – fecal wet weight output. Changes from baseline to Week 24 (Visit 9) will be measured.

# 8.2.6 Absorption of Energy

During both 48-hour metabolic balance studies (Visit 1 and Visit 9) the processed dry matter for the duplicate meal and all liquid intake and the fecal output will be analyzed for energy content by bomb calorimetry. Absorption of energy is measured as oral intake (liquid and solid) minus fecal output. Changes from baseline to Week 24 (Visit 9) will be measured.

# **8.2.7 Absorption of Macronutrients**

During both 48-hour metabolic balance studies (Visit 1 and Visit 9), the processed dry matter for the duplicate meal and all liquid intake and the fecal output will be analyzed for macronutrients: fat by titration, carbohydrate by Englyst's method (33) and nitrogen by Kjeldahl's method (34). Energy will be assessed by bomb calorimetry. Absorption of macronutrients is measured as oral intake (liquid and solid) minus fecal output. Changes from baseline to Week 24 (Visit 9) will be measured.

# 8.2.8 Absorption of Electrolytes

During both 48-hour metabolic balance studies (Visit 1 and Visit 9), the homogenized wet weight of the duplicate meal and all liquid intake and the fecal output will be analyzed for electrolytes. Absorption of electrolytes is measured as oral intake (liquid and solid) minus fecal output. Changes from baseline to Week 24 (Visit 9) will be measured.

### 8.2.9 Weekly PS Volume (SBS-IF Only)

During the trial, PS volume and content will be regulated according to changes in urine output, weight change and clinical symptoms of fluid overload. During the second part of the trial, this will be based on a 48-hour measurement without a fixed drinking menu. Changes from baseline to Week 12 (Visit 6), Week 24 (Visit 9) and Week 52 (Visit 12) will be measured.

### **Requirement for PS volume reduction:**

IF: daily urine volume of the current visit is at least 10% higher than baseline urine volume.

Quantity of PS volume reduction:

THEN: New PS volume (weekly) = Current PS volume (weekly) -7 x absolute increase in daily urine volume.

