### Figure 1 Overall Trial Design

The trial consists of a screening period, a treatment period and a follow-up period.

After signing informed consent, patients will be screened for initial confirmation of eligibility. The screening procedures should be performed within 3 weeks prior to Visit 1 (baseline).

At Visit 1, eligible patients will complete a 48-hour in-house (admission to the hospital, at site) baseline metabolic balance study as well as other baseline assessments, where after they will start treatment with glepaglutide 10 mg once-weekly for 52 weeks. The treatment period covers 12 visits at the week numbers indicated in Figure 1.

All patients will have in-house stays for 48-hour metabolic balance studies at baseline and at Visit 9; see Figure 1. During the in-house periods, they must follow an individual drinking menu, but may vary the food intake according to their own choice.

All patients will have a 48-hour period scheduled before each Visit (except Visit 1 and 9 where balance studies are done), during which they must record their fluid intake and urine output. During the screening phase, all patients need to construct an individual fixed drinking menu to be kept during all 48-hour "pre-visit" periods until Visit 9. The same individual drinking menu will be followed during both scheduled in-house 48-hour metabolic balance studies (at Visit 1 and 9). After Visit 9, the patients are no longer restricted to a fixed drinking menu during the 48-hour periods, but they should instead drink an amount that reflects their preferred or habitual fluid intake. They must only drink the same fluid items as in the drinking menu and must record their intake as well as their urine output. Patients receiving PS (patients with SBS-IF) will have their PS adjusted based on an algorithm which will be used at each visit (see section 8.2.9).

A follow-up visit will be performed 4 weeks after end of treatment.

For each patient the trial period will be a maximum of 59 weeks.

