### Example:

Patient received so far 10 L of PS per week. The urine output has increased from 1300 mL per day to 1500 mL per day. Hence, the urine output has increased by more than 10% and PS volume should be reduced. The new weekly PS volume should be 8.6 L (10 L - 7 x 200 mL).

PS volume and content may be changed for safety reasons, e.g. if clinical signs of laboratory values support this or in case of clinical signs of fluid overload, as judged by the Investigator.

In cases where a patient may not have been fully compliant with the adherence to the prescribed PS volume, the drinking menu, and/or may have missed a urine measurement (e.g., in case the patient has missed to report a urine measurement during the 48-hour measurement period), the Investigator may still perform adjustments to the new PS volume at the Investigators discretion, in order to best match the needs of the patient and in adherence with the algorithm stated above. In that case, the reason for the change must be documented in the eCRF.

The patients should be instructed to contact the clinical site in case urine production falls below normal and if their clinical status changes.

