### Increasing PS volume:

Increasing PS volume should be considered if laboratory parameters indicate safety concerns. If the average urine production falls below 1 L per day, the Investigator should consider increasing PS volume.

If PS is not adjusted according to the algorithm (within  $\pm 200$ mL/day) a reason for not adhering to the algorithm must be provided in the eCRF.

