• Absorption of electrolytes (sodium, potassium, calcium and magnesium): Change from baseline to Week 24 measured by 48-hour metabolic balance studies.

Absorption of electrolytes during the MBS at V1 and V9 is measured as oral intake (liquid and solid) minus fecal output.

Then Absorption of Electrolytes: Sodium (mmol/d) is calculated as

Absorption of Electrolytes: Sodium (mmol/d) =

Electrolytes: Sodium intake (mmol/d) - Electrolytes: Sodium fecal output (mmol/d)

The calculation of the following items

- Electrolytes: Sodium intake (mmol/d)
- Electrolytes: Sodium fecal output (mmol/d)

is done as described in Section 2.2.3.

Absorption of Electrolytes: Sodium (mmol/d) will be analyzed at Baseline and Week 24. Change from baseline to Week 24 for Absorption of Electrolytes: Sodium (mmol/d) is calculated as described in Section 2.1.2 and will be analyzed at Week 24.

Furthermore,

- Absorption of electrolytes: Potassium (mmol/d),
- Absorption of electrolytes: Calcium (mmol/d) and
- Absorption of electrolytes: Magnesium (mmol/d)

as well as their changes from baseline to Week 24 are calculated and analyzed analogously to Absorption of Electrolytes: Sodium (mmol/d) and its change from baseline to Week 24.

- For patients with Short Bowel Syndrome with Intestinal Failure (SBS-IF) only:
 - Weekly parenteral support (PS) volume: Change from baseline to Week 12 and 24.

PS volumes (mL) are documented by the patient in the diary and then transcribed to the eCRF page "Diary PS use". Weekly PS volume (mL) at a certain visit is calculated as sum of PS volumes (mL) for all PS bag ids over the seven days of the preceding week (date of visit -1 to date of visit -7) based on the information in the eCRF.

Here the date of visit used at baseline is the date of Visit 1 – Week 0 – Day 4 as documented in the eCRF. At Week 24, the date of Visit 9 – Week 24 – Day 4 is used. Weekly PS volume (mL) will be missing, in case any unknown volume is documented.

In case information on Diary PS use in the week before the baseline visit is available for less than seven days, weekly PS volume (mL) at baseline is determined based on prescribed PS over the seven days before the date of Visit 1 – Week 0 – Day 4. Thus, all PS prescriptions which are valid on date of "Visit 1 – Week 0 – Day 3" are determined. Then, the Weekly PS volume (mL) at baseline is calculated as sum of all weekly volumes (L) for these prescriptions as documented in the eCRF and multiplied by 1000.

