2-3.11.1.1.1- 2-3.11.1.1.4	Urinary excretion of electrolytes: Change from baseline to Week 24 - Sodium [mmol/d] - Potassium [mmol/d] - Calcium [mmol/d] - Magnesium [mmol/d]	FAS / PPS
2-3.11.1.2.1- 2-3.11.1.2.4	Urinary excretion of electrolytes by visit - Sodium [mmol/d] - Potassium [mmol/d] - Calcium [mmol/d] - Magnesium [mmol/d]	FAS / PPS
2-3.11.2.1	Urinary excretion of urea [mmol/d]: Change from baseline to Week 24	FAS / PPS
2-3.11.2.2	Urinary excretion of urea [mmol/d] by visit	FAS / PPS
2-3.12.1	Fluid composite effect [L/d]: Change from baseline to Week 12, 24 and 52	FAS / PPS
2-3.12.2	Fluid composite effect [L/d] by visit	FAS / PPS
2-3.13.1	Drinking volume during 48-hour periods: Change from Week 24 to 52	FAS / PPS
2-3.13.2	Drinking volume during 48-hour periods by visit	FAS / PPS
2-3.14	Weekly parenteral support volume: Change from baseline to Week 52 (SBS-IF only)	FAS / PPS
2-3.15.1- 2-3.15.7	Weekly parenteral support macronutrients and electrolytes (SBS-IF only): Change from baseline to Week 52 - Macronutrient: Carbohydrates [kjoule] - Macronutrient: Lipids [kjoule] - Macronutrient: Proteins [kjoule] - Macronutrient: Total content [kjoule] - Electrolyte: Sodium [mmol] - Electrolyte: Potassium [mmol] - Electrolyte: Magnesium [mmol]	FAS / PPS
2-3.16.1	Weekly days on PS: Change from baseline to Week 12, 24, and 52 (SBS-IF only)	FAS / PPS
2-3.16.2	Weekly days on PS by visit (SBS-IF only)	FAS / PPS

No.	Title/Content	Analysis Sets
2-3.17.1	Urine output: Change from baseline to Week 12, 24 and 52 (SBS-II only)	FAS / PPS
2-3.17.2	Urine output by visit (SBS-II only)	FAS / PPS

No.	Title/Content	Analysis Sets
3. Safety Ev	valuation	
3-1.1	Number of patients with different adverse event categories, overview	SAS
3-1.2	Treatment-emergent adverse events by MedDRA System Organ Class (SOC) and Preferred Term (PT)	SAS
3-1.3	Treatment-emergent adverse drug reactions by MedDRA System Organ Class (SOC) and Preferred Term (PT)	SAS
3-1.4	Treatment-emergent serious adverse events by MedDRA System Organ Class (SOC) and Preferred Term (PT)	SAS
3-1.5	Adverse events leading to permanent discontinuation of study treatment by System Organ Class (SOC) and Preferred Term (PT)	SAS
3-1.6	Treatment-emergent adverse events by severity, seriousness, relationship, action taken with study treatment, and outcome, overview	SAS
3-1.7	Treatment-emergent adverse events by severity and Preferred Term (PT)	SAS

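### The one-directional PS reduction formula tends to lower weekly PS volume even with no drug effect, and no summary table shows SBS-IF urine volume beside it

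*Protocol*

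**What the plan says.** **Reduction (Protocol 8.2.9).** The condition is "IF: daily urine volume of the current visit is at least 10% higher than baseline urine volume". The amount is "New PS volume (weekly) = Current PS volume (weekly) -7 x absolute increase in daily urine volume". Under Protocol 4.1, SBS-IF patients "will have their PS adjusted based on an algorithm which will be used at each visit".

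**Increase (Protocol 8.2.9).** There are two prompts and no formula: "Increasing PS volume should be considered if laboratory parameters indicate safety concerns", and "If the average urine production falls below 1 L per day, the Investigator should consider increasing PS volume". Neither gives an amount or refers to the patient's own baseline urine. The section also names weight change and symptoms of fluid overload, allows changes for safety, and asks for a documented reason when an adjustment departs from the algorithm by more than 200 mL/day.

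**Analysis.** SAP 2.3.2 lists "Weekly parenteral support (PS) volume: Change from baseline to Week 12 and 24" among the secondary efficacy endpoints, and Week 52 is exploratory. SAP 4.3.3 plans descriptive statistics on the FAS, with no reference value. Protocol 6.3 presents the algorithm as a limit on open-label bias.

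**Tables (SAP Appendix A).** Urine output (2-3.17.1 and 2-3.17.2) is tabulated for SBS-II only. The Fluid Composite Effect, PS/7 + oral fluid - urine, is tabulated at Weeks 12, 24 and 52 (2-3.12.1 and 2-3.12.2), and SAP 4.1 splits tables by SBS type. Patient-level drinking and urine volumes for both types are in Listing 2-6.

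**The concern.** The reference for every cut is one 48-hour urine measurement, which carries its own error for the whole trial. If it happens to be low, later visits exceed it by 10% more easily. If a later visit happens to be high, PS is cut by the full excess. A chance low value later produces no mirror-image correction; at most it prompts a discretionary one. Repeated at each visit, this moves weekly PS downward without any change in absorption.

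With no control arm, the reported change from baseline mixes this drift with any drug effect, and both point the same way. Where PS was cut on noise and the lost fluid shows in the urine, SBS-IF urine should fall below baseline. That would be the most direct sign, and it is not summarised for the group whose PS is adjusted on urine.

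**Working it through.** **Plan's own figure.** Baseline 1300 mL/day, current 1500 mL/day, PS 10 L/week. The threshold is 1.1 x 1300 = 1430 mL/day, so the rule applies. New PS = 10 - 7 x (1.5 - 1.3) = 8.6 L/week, as the protocol states.

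**Inputs from the documents.** Starting urine 1.3 L/day and PS 10 L/week (the 8.2.9 example). The rule is used at each visit and PS is read over the seven days before the visit. That gives 4 applications before the Week 12 reading (V2-V5), 7 before Week 24 (V2-V8) and 10 before Week 52 (V2-V11).

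**Assumptions, not in the documents.** Within-patient CV of 48-hour daily urine of 5-30%, with independent normal errors. A pass-through fraction c, the share of a PS change that appears in urine (1 or 0.5). Exact application of the formula.

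**Chance of a cut at one visit, no effect.** Let B be baseline urine and U current urine, with the same true mean and CV v. Then P(U >= 1.1B) = 1 - Φ(0.1 / (v x √(1 + 1.1²))) = 1 - Φ(0.1 / 1.487v). At v = 15% this is 1 - Φ(0.448) = 33%.

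**Simulated no-effect change at Week 24 (c = 1).** U = true mean + c x (PS - 10)/7 + error, with the formula applied at V2-V8. In the last column PS is also raised by 7 x the shortfall below 1 L/day every time; that amount is assumed, because the protocol gives none.

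| Urine CV | Cut at one visit | No increases (L/week) | 1 L/day clause always acted on (L/week) |
|---|---|---|---|
| 5% | 9% | -0.35 | -0.34 |
| 10% | 25% | -1.09 | -0.77 |
| 15% | 33% | -1.78 | -0.91 |
| 20% | 37% | -2.47 | -1.00 |

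At CV 30% the two columns become -3.77 and -1.07. With c = 0.5 and no increases, the range over CV 5-30% is -0.39 to -4.71.

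**Over time (CV 15%, c = 1).** Without increases the change is -1.44, -1.78 and -1.99 L/week at Weeks 12, 24 and 52. At Week 24, 70% of patients are below baseline PS and 42% are down by at least 20%. With the clause always acted on it is -0.88, -0.91 and -0.92, and 17% are down by at least 20% at Week 24.

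**Source of the drift.** Making the formula symmetric, purely as a diagnostic, brings the mean change to between -0.03 and 0.00 L/week at c = 1. The asymmetry is therefore the cause. This is not a proposal for PS management.

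**What the other summaries would show under no effect.** With oral fluid fixed, the urine change is c x ΔPS/7 and the composite change is (1 - c) x ΔPS/7. At CV 15%, c = 1 and no increases, urine falls by 1.78/7 = 0.254 L/day while the composite stays near 0 (0 to -26 mL/day at Week 24 across the CVs run). At c = 0.5 the composite itself drifts by -28 to -339 mL/day.

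**The case against.** Four points can fairly be made for the plan.

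1. **The rule is not unguarded.** A reader might infer that any upward swing cuts PS and that nothing can restore it. The documents do not support that. A 10% rise is required, the increase clause exists, and weight, symptoms and safety also enter. The 48-hour average, the fixed drinking menu up to Visit 9 and same-weekday timing should reduce noise. These shrink the drift. They did not remove it in any scenario that applied the written formula.

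2. **A planned table already helps.** Under full pass-through, a noise-driven cut appears as lower PS with an unchanged composite. Mean SBS-IF urine can also be recovered as PS/7 + daily oral volume - composite when the same patients contribute to each table, and with about five SBS-IF patients (10 planned, equal split intended) Listing 2-6 can be read directly. So it would be wrong to say that the SAP offers no check. But the composite is clean only if c is near 1, and no table shows the urine component.

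3. **The larger figures depend on assumptions.** They assume that PS is never increased, and neither CV nor pass-through is documented. If PS is instead raised by the full shortfall from baseline whenever urine is below both 1 L/day and baseline, the drift at 1.3 L/day is only about -0.3 to -0.5 L/week at CV 5-20%. The 200 mL/day tolerance is not modelled. This stands: only the direction is firm.

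4. **Stakes are limited.** Weekly PS volume is descriptive and outside the testing hierarchy, and absorption is measured directly by balance study at Week 24. This stands too.

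**Conclusion.** The concern holds as a bias of known direction and unknown size in a non-confirmatory efficacy endpoint. Using the protocol's example values, full pass-through and assumed CVs of 5-20%, the no-effect change at Week 24 is about -0.3 to -2.5 L/week without increases, and about -0.3 to -1.0 L/week if the 1 L/day clause is always acted on by the assumed amount.

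Two stronger conclusions might be drawn, and neither is supported. The first is that an observed PS reduction would be mostly artefact: the documents give no urine variability or pass-through from which to say so. The second is that the trial's main result is compromised: the primary and key secondary tests use wet weight and energy absorption from the balance studies, not PS volume.

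Protocol 6.3 is right that an algorithm limits discretion. It does not follow that the resulting PS change is unbiased.

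**What to change.** 1. **Table.** Extend Tables 2-3.17.1 and 2-3.17.2 to SBS-IF at Weeks 12, 24 and 52, and present them beside weekly PS volume and the SBS-IF fluid composite. The urine volumes are already collected.

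2. **Reading rule in SAP 4.3.3.** State that a PS reduction is read as improved absorption only where SBS-IF urine is maintained and the composite falls, and define in advance what counts as maintained. Note that the one-directional rule lowers PS even with no effect. Both conditions are needed, because the composite alone drifts at partial pass-through. Even together they discriminate poorly if pass-through is low, since urine then hardly falls.

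3. **Optional sensitivity range.** Report the no-effect drift over stated, assumed urine CVs and pass-through values. A benchmark built from each patient's own urine variation is not advised. There is only one pre-treatment 48-hour period, and later values mix drug effect, PS changes and, after Visit 9, free drinking.

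The cost is one extended table pair, a few sentences in the SAP and, if wanted, a short simulation. The PS result will read slightly less favourably. The clinical PS rule is left as it is.
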